5.0 Statistical and Power Analyses

5.1 Sample Size Justification

Sample size estimates are based on the mean changes and standard deviations in GI tolerability score observed in the study of adult subjects taking the MM [27] including a mean tolerability score of 7 with standard deviation 4. Using alpha 0.05 with 80% power, we will need 10 participants to complete the study. Assuming a 50% attrition rate for this crossover study, we expect to recruit approximately 20 individuals. For the secondary outcome, our preliminary data reporting a mean change of $2.95\pm3.3 \mu mol/g$ of proprionate and $4.17\pm5.72 \mu mol/g$ of butyrate (Figure 3), 20 participants will achieve 90% power, assuming an α =0.05, and correlation coefficient of 0.5.

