stimulating the growth and/or activity of one or a limited number of bacteria in the colon, thus improving host health" [20]. These supplements are effective in reducing the severity and duration of infectious diarrhea [21], as well as improving bowel regularity. Prebiotics may also improve intestinal permeability and gut inflammation - two factors which have been linked to obesity and metabolic syndrome [22, 23]. However, prebiotic supplements, when used in isolation, could increase flatulence by producing methane and hydrogen sulfide gas as byproducts via methanogen and sulfate-reducing bacteria, respectively (Figure 2) [24]. To decrease these unwanted side effects, preliminary studies have demonstrated that using polyphenols -- naturally occurring compounds that are metabolized by the SCFA-producing bacteria (acetogens)-- may be helpful in reducing flatulence (Figure 2) [25]. The presence of polyphenols, commonly found in fruits and vegetables, allows acetate-producing bacteria to thrive, while methane- or hydrogen sulfate-producing bacteria have less available hydrogen substrate to convert to their respective gases [25, 26]. In a pilot randomized trial of 10 adults with T2D, a prebiotic microbiome modulator (MM) with inulin and beta glucan plus polyphenols from blueberry pomace improved metformin tolerability and fasting glycemia [27]. This same cocktail improved glucose profiles in healthy adults with overweight and obesity during an oral glucose tolerance test [28]. However, the mechanisms by which prebiotics influence metformin-induced GI side effects are unknown. Importantly, it remains to be established whether using this supplement is feasible in youth and young adults with T2D, whose microbiome signatures may be different from adults [29]. This study is innovative and clinically significant because it uses a prebiotic intervention to evaluate gut-incretin pathways while identifying whether a relatively safe supplement could

improve quality of life and glycemia in youth and young adults with type 2 diabetes who are high-risk for diabetesrelated complications.

Preliminary studies:

Currently, we are exploring metformin's mechanism of action in African American youth with T2D (NCT02960659), including changes in their microbiome. Our preliminary findings from 4 youth who were evaluated before and after 3-months of metformin therapy showed a decreasing trend for HbA1c (-0.56±0.2%) and increasing trends for stool

[figure not shown]

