2.0 Specific Objectives/ Aims

The primary objective of this study is to determine the feasibility and efficacy of a prebiotic MM to improve metformininduced lower GI side effects in youth with T2D and the secondary objective is to measure the change in stool SCFA content after prebiotic MM intervention.

Aim 1. To compare lower-GI side effects and stool consistency (tolerability score) in youth and young adults with T2D at initiation of daily metformin therapy when used with a daily prebiotic microbiome modulator (MM) vs placebo over a 1-week period.

Hypothesis: A prebiotic MM will be associated with higher tolerability scores (a composite score of lower GI-related side effects and stool consistency) compared to placebo.

Rationale: A prebiotic MM, containing both fiber and polyphenols, reduced metformin-related GI side effects in adults with T2D while retaining, and even augmenting, the hypoglycemic effects expected with metformin therapy in a small study (4). Due to the significant potential for clinical benefit, we propose to validate these results in youth, in whom metformin is the only FDA approved anti-diabetic therapy.

Aim 2. To compare the change in SCFA stool content in youth with T2D on metformin therapy when treated with prebiotic MM vs. placebo after 1 week and 4 weeks.

Hypothesis: The prebiotic MM will be associated with higher SCFA stool content compared to placebo. **Rationale**: SCFAs are microbial metabolites derived from fermentation of dietary fibers that are likely gut mediators of glucose metabolism. Metformin and prebiotic fiber individually have been demonstrated to increase stool SCFA [13, 16, 30, 31]. We propose to further elucidate the mechanism of metformin and MM, both individually and when taken together. **Exploratory aims:** To evaluate the relationship of change in tolerability score with change in stool SCFA, change in gut microbial diversity and SCFA-producing phyla, change in intestinal permeability markers, determine tolerability score for metformin and prebiotic MM over 1 month, and change in measures of glucose, insulin and incretin kinetics after treatment with placebo compared to 4 weeks of continuous prebiotic MM intervention.

[figure not shown]

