3.0 Study Design

3.1 Study Design and Timeline

This 9-week pilot study will have 2 phases and 6 outpatient visits at the NIH Clinical Center (Figure 4). Phase 1 is a 5week randomized double-blind randomized cross-over trial with two 1-week intervention periods (metformin + prebiotic and metformin + placebo). Phase 2 will occur immediately following phase 1 in which participants will start an openlabel 4-week intervention with metformin and the prebiotic MM.

Phase 1: This is a randomized double-blind cross-over study of youth with T2D with two intervention periods (metformin + prebiotic MM BiomeBliss® ®, and metformin + placebo). Participants will have 5 study visits over the 5-week period. After screening history and physical examination are performed at visit 1, participants will enter a 1-week run-in period in which metformin therapy will be discontinued and blood glucose will be monitored twice daily via finger stick or with a continuous glucose monitor. The order of intervention will be randomized at Visit 2; when initiating metformin, participants will have 1-3 days of dose escalation, then arrive at a final dose of 850mg twice daily. After 7-9 days of treatment, participants will be evaluated as described in Table 1, then enter a 2-week washout period of prebiotic/placebo and metformin, and then cross over to the opposite intervention for 1 week.

Phase 2: This is an open-label 4-week extension of metformin + prebiotic MM. Participants will receive a 1-month supply of metformin and prebiotic at the end of Phase 1 (Visit 5) and be evaluated for measures of stool metabolite and glycemia at the end of the trial (Visit 6).

Every effort will be made to adhere to the proposed timelines, but some flexibility is required for scheduling of other studies, unanticipated equipment maintenance, etc. Scheduling variations will not be reported.

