5.2 Analysis of Primary and Secondary Outcomes

The primary outcome, the participant's composite score of tolerability will be constructed using the principal component analysis (PCA) based on 4 GI side effect profile categories (stool consistency, urgency to evacuate, bloating sensation, and flatulence). PCA will be used to account for the expected high inter-patient variability. Comparison of mean tolerability score over 1 week will be with linear mixed models, adjusting for baseline score. Pre-specified covariates are: treatment period and sequence effects from the cross-over design.

The secondary outcome, change in mean stool SCFA over 1 and 4 weeks, will be analyzed using repeated measures of analysis variance (ANOVA) to consider correlation of observations within each participant. Participant and exploratory characteristics will be expressed as mean and standard deviation, median and interquartile range for continuous variables and frequency for categorical variables. Between group comparison of means will also be analyzed using repeated measures ANOVA. Spearman correlations will be used to compare relationships between continuous variables. A P-value of <0.05 will be used for statistical significance.

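### The 90% power claimed for stool SCFA uses the 20 participants recruited; at the 10 expected to complete, neither acid reaches 90%

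*Combined protocol and SAP*

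**What the plan says.** Section 5.1 sizes the trial on the primary outcome: "we will need 10 participants to complete the study". It continues: "Assuming a 50% attrition rate for this crossover study, we expect to recruit approximately 20 individuals". For the secondary outcome it takes mean changes of 2.95 ± 3.3 µmol/g for propionate and 4.17 ± 5.72 µmol/g for butyrate from preliminary data and concludes that "20 participants will achieve 90% power", "assuming an α =0.05, and correlation coefficient of 0.5". It names neither the test nor its sidedness.

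The hypothesis for Aim 2 in section 2.0 is that "The prebiotic MM will be associated with higher SCFA stool content compared to placebo". Under section 5.2 the SCFA outcome "will be analyzed using repeated measures of analysis variance (ANOVA) to consider correlation of observations within each participant", with P<0.05 as the threshold. Section 1.0 gives the source of the planning data: "Our preliminary findings from 4 youth who were evaluated before and after 3-months of metformin therapy".

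**The concern.** The same paragraph that expects half of 20 recruits to be lost credits all 20 with SCFA power. Nothing in sections 5.1 or 5.2 plans for 20 completers or describes imputation of missing SCFA values. If the 90% belongs to 20 analysed participants, it does not describe the data that the plan expects to have.

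This is the only figure in the protocol for how informative the Aim 2 comparison will be. A reader who relies on it would take a null butyrate result as coming from a comparison with a 10% chance of missing the assumed effect, when that chance would be several times larger.

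The inputs raise a second question. Both crossover periods include metformin (section 3.1), so a before/after change on metformin is not the contrast that Aim 2 tests.

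**Working it through.** **Inputs (section 5.1).** Mean change and SD: propionate 2.95 and 3.3; butyrate 4.17 and 5.72 µmol/g. Alpha 0.05, correlation 0.5, 20 recruited, 50% attrition, so 20 × 0.5 = 10 completers. The ± is read as an SD.

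**Effect size.** In a crossover the comparison is within person. If the stated SD is that of a single measurement, SD of the difference = SD × √(2(1 − 0.5)) = SD. If it is already the SD of the change, it is used directly. Both readings give the same standardised effect:

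- propionate d = 2.95/3.3 = 0.894
- butyrate d = 4.17/5.72 = 0.729

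**Reproducing the 90%.** Two-sided normal approximation: power = Φ(d√n − 1.960).

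- Butyrate, n = 20: Φ(3.260 − 1.960) = 90.3%. The n required for 90% is (1.960 + 1.282)²/0.729² = 19.8, which rounds up to 20.
- Propionate, n = 20: Φ(3.998 − 1.960) = 97.9%.

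The stated figure therefore matches butyrate, the more demanding acid, with 20 analysed pairs and no attrition.

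**Applying the plan's attrition.** Same formula, n = 10:

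- Propionate: Φ(2.827 − 1.960) = 80.7%
- Butyrate: Φ(2.305 − 1.960) = 63.5%, a loss of about 27 points

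**Other readings.** Section 5.1 names no method or sidedness, so four readings were computed. The t versions use the noncentral t with n − 1 degrees of freedom. For two conditions, the repeated measures ANOVA F test is the two-sided paired t test.

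| Reading | Propionate, n = 20 | Propionate, n = 10 | Butyrate, n = 20 | Butyrate, n = 10 | Pairs for 90% (propionate / butyrate) |
|---|---|---|---|---|---|
| Two-sided normal | 97.9% | 80.7% | 90.3% | 63.5% | 14 / 20 |
| Two-sided paired t | 96.6% | 71.1% | 87.1% | 53.9% | 16 / 22 |
| One-sided normal | 99.1% | 88.1% | 94.7% | 74.6% | 11 / 17 |
| One-sided paired t | 98.6% | 83.2% | 93.3% | 68.5% | 13 / 18 |

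No entry at n = 10 reaches 90%. Using n − 2 degrees of freedom to allow for a period effect lowers the two-sided t figures slightly, to 69.8% and 52.7%.

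**Detectable difference.** With 10 pairs, 80% power and a two-sided paired t test, d = 0.996. At the stated SDs this is 0.996 × 3.3 = 3.29 µmol/g for propionate (input 2.95) and 0.996 × 5.72 = 5.70 µmol/g for butyrate (input 4.17).

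**The case against.** **The sentence is a correct conditional: 20 participants do give about 90%.** The calculation does reproduce. The error is in the number used: the paragraph has just said that 20 is the recruited number and that half will not complete.

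**Ten may understate the evaluable pairs at 1 week.** Someone lost during the open-label phase would still have both Phase 1 stool samples, and the documents do not say when the 50% is lost. This stands as a caveat. If 15 pairs were available (an assumption), the two-sided normal approximation gives 93.3% for propionate and 80.6% for butyrate; the two-sided paired t gives 89.6% and 74.7%. Butyrate stays below 90% on all four readings, at most 88.1%.

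**Quoting the paired t adds a change of method to the attrition correction.** That is fair: at 10 pairs the move from normal to t takes off a further 10 points or so. The like-for-like fall is the 90.3% to 63.5% shown above, and it is enough to make the point. The ANOVA may also cover more than two conditions, since the outcome is assessed at 1 and 4 weeks. The paired t represents the 1-week MM-versus-placebo contrast.

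**New power figures from 4 youth are themselves fragile.** This also stands. A normal-theory 95% interval for an SD from n = 4 runs from about 0.57 to 3.73 times its value. With the means held fixed, two-sided t power at 10 pairs then runs from about 10% to 99% for propionate and 9% to 95% for butyrate. Any restated power must be conditional on the inputs, and the detectable difference in SD units is the sturdier statement.

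**This is a pilot, and SCFA did not set the sample size.** True, and a pilot need not have 90% power. But a power that is stated should match the data expected.

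**Conclusion.** The concern holds. The 90% is a power for about 20 analysed participants, while the plan expects 10. On the method that reproduces it, the plan's own attrition lowers butyrate from 90.3% to 63.5% and propionate from 97.9% to 80.7%. Over the four readings, power at 10 completers is 71–88% for propionate and 54–75% for butyrate. Reaching 90% takes 11 to 16 completers for propionate and 17 to 22 for butyrate.

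These figures rest on three assumptions: the ± is an SD, the 50% attrition leaves 10 usable pairs, and MM exceeds placebo by the stated amounts. The documents do not support the third, because the inputs describe 3 months of metformin and not MM added to metformin. The consequence is limited to a planning statement for a secondary outcome; no estimate or error rate changes. It should still be corrected.

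**What to change.** Replace the SCFA power sentence in section 5.1 with text to this effect:

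> With the expected 10 completers, a two-sided paired t test at alpha 0.05 has about 71% power for propionate and 54% for butyrate, if MM exceeds placebo by 2.95 and 4.17 µmol/g with SDs of the within-person difference of 3.3 and 5.72 µmol/g. Ten completers give 80% power for a within-person difference of about 1.0 SD, or about 3.3 and 5.7 µmol/g at these SDs. The planning values are before/after changes over 3 months of metformin in 4 youth and do not estimate an MM-versus-placebo difference.

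If the sponsor expects more than 10 evaluable pairs at 1 week, it should state that number with its reason and give the power for it.

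The cost is wording in section 5.1 and a less favourable stated power. Enrolment, the planned analysis and the P<0.05 rule stay unchanged.

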Figure 3. Stool short Chain Fatty Acid Concentrations in feces before and after 3 months of metformin therapy in youth with type 2 diabetes (n=4).

propionate and butyrate (P=0.1, Figure 3). In collaboration with [name] at Wake Forest, using 16S Ribosomal targeted sequencing and Qiime analysis of Operational Taxonomic Units (OTUs), we also observed modest changes in microbial diversity, a decreasing trend in the Shannon index (an index of complexity, P=0.15). This decreased diversity has been seen in other studies of metformin-induced changes in the gut

microbiota [14]. Therefore, metformin may change gut microbial diversity in association with changes in SCFA stool concentrations in youth, but larger samples sizes are needed

for confirmation. While metformin alone can increase SCFA, prebiotic MM may be able to augment this increase by shifting substrate metabolism away from gas (hydrogen sulfide and methane) to acetate production. Further investigations into these mechanisms will help us determine the feasibility of an oral supplement to mitigate side effects of metformin and improve quality of life, as well as glycemia, in youth with T2D.

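### The 90% power for stool SCFA is computed for metformin's own before-after change, not for the added effect of the prebiotic MM that the 1-week crossover tests

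*Combined protocol and SAP*

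**What the plan says.** Section 5.1 (Sample Size Justification) introduces the SCFA calculation with "For the secondary outcome, our preliminary data reporting a mean change of" 2.95 ± 3.3 µmol/g for propionate and 4.17 ± 5.72 µmol/g for butyrate, and cites Figure 3. It concludes that "20 participants will achieve 90% power", "assuming an α =0.05, and correlation coefficient of 0.5".

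The preliminary-studies text in Section 1.0 gives the source of those data: "Our preliminary findings from 4 youth who were evaluated before and after 3-months of metformin therapy". The caption of Figure 3 agrees. None of the measurements is described as taken on MM or on placebo.

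Aim 2 in Section 2.0 is "To compare the change in SCFA stool content in youth with T2D on metformin therapy when treated with prebiotic MM vs. placebo", at 1 week and at 4 weeks, with the hypothesis that MM gives the higher SCFA content. Section 3.1 describes two 1-week crossover periods, one of metformin with MM and one of metformin with placebo, followed by 4 open-label weeks of metformin with MM. Section 5.2 analyses the change in mean SCFA over 1 and 4 weeks by repeated-measures ANOVA.

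**The concern.** The effect used for planning and the effect to be tested are different quantities. The pilot change measures what metformin does to stool SCFA over 3 months. The crossover contrast measures what MM adds to metformin over 1 week. Because metformin is in both periods, its main effect is common to the two measurements and cancels from the within-person difference. Any MM effect, including an interaction with metformin, remains, and the pilot data carry no information on it. Section 1.0 says only that MM may augment the metformin rise. It gives no size, and nowhere do the documents argue that the metformin change can stand in for the MM effect.

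The protocol thus attaches a high power to a named secondary outcome without support for the effect assumed. A reader who relies on that figure could take a non-significant SCFA result as stronger evidence against an MM effect than the design allows.

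**Working it through.** **Inputs (Section 5.1).** Propionate: mean change 2.95, SD 3.3. Butyrate: mean change 4.17, SD 5.72 (µmol/g). n = 20, alpha 0.05, correlation 0.5. The section does not say whether alpha is two-sided or whether ± is an SD. Two-sided and SD are assumed here.

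**SD of the paired difference.** SD_diff = SD × √(2(1 − 0.5)) = SD. Reading ± as the SD of the change or as the SD at each occasion therefore gives the same result.

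**Standardised effects.** 2.95/3.3 = 0.894; 4.17/5.72 = 0.729.

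**Reproducing the plan's figure.** Normal approximation: power = Φ(d√n − 1.96).
- Butyrate: 0.729 × √20 = 3.260; Φ(1.300) = 90.3%.
- Propionate: 0.894 × √20 = 3.998; Φ(2.038) = 97.9%.

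The exact paired t (noncentral t, 19 df) gives 87.1% and 96.6%. The butyrate result matches the stated 90%. Two independent groups of 20 would give only 61% (butyrate) and 79% (propionate). The 90% is thus consistent with a paired calculation in which the metformin before-after change is the difference to be detected. The arithmetic is sound; the effect put into it is the problem.

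**How large must the MM effect be?** With 20 pairs, the exact paired t reaches 90% power at 2.52 µmol/g for propionate (2.52/2.95 = 85% of the metformin change) and 4.37 µmol/g for butyrate (4.37/4.17 = 105%).

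**Power if MM adds a fraction f of the metformin change.** The fractions are assumptions, since the documents give no MM effect on SCFA. They run both ways because nothing in the documents caps the MM effect at metformin's. Exact paired t, two-sided 0.05, SD_diff as above:

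| f | Propionate, 20 pairs | Butyrate, 20 pairs | Propionate, 10 pairs | Butyrate, 10 pairs |
|---|---|---|---|---|
| 0.5 | 48% | 34% | 24% | 18% |
| 1.0 | 97% | 87% | 71% | 54% |
| 1.5 | >99% | >99% | 96% | 87% |

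The 10-pair columns reflect the 10 completers that Section 5.1 plans for after 50% attrition. That is a separate matter; the choice of effect is at issue even if all 20 complete.

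**Precision under the same SDs.** Half-width of the 95% CI = t(0.975, n − 1) × SD/√n.
- 10 pairs: 2.262 × 3.3/√10 = 2.4; 2.262 × 5.72/√10 = 4.1.
- 20 pairs: 2.093 × 3.3/√20 = 1.5; 2.093 × 5.72/√20 = 2.7.

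The difference detectable with 80% power is 0.996 SD with 10 pairs (3.3 / 5.7 µmol/g) and 0.660 SD with 20 pairs (2.2 / 3.8 µmol/g).

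**How firm are the SDs?** A normal-theory 95% interval for an SD estimated from 4 people runs from 0.57 to 3.73 times the estimate. The half-widths with 20 pairs could therefore lie anywhere from 0.9 to 5.8 (propionate) and 1.5 to 10.0 (butyrate). If ± is a standard error, the SD doubles (√4 = 2), and power at the full metformin change with 20 pairs falls to 48% / 34%.

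**The case against.** The strongest reply is that a metformin before-after change is not foreign to this trial. Stool is collected off metformin at Visits 2 and 4 and on treatment at Visits 3, 5 and 6. Section 5.2 defines the outcome as a change and names no placebo contrast, and the rationale for Aim 2 speaks of metformin and MM both separately and together. This stands in part: it would be too strong to say that the trial cannot estimate such a change. But the leading sentence of Aim 2 and its hypothesis are MM against placebo, and a before-after change within a period would be at 1 week, not 3 months.

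A second reply is that the cancellation argument does not reach the 4-week part of Aim 2. That is correct. Phase 2 has no concurrent placebo, and a 4-week change from an off-metformin baseline mixes metformin and MM effects. The point is therefore limited to the 1-week contrast.

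Third, this is a pilot, and the recruitment of 20 follows from the primary outcome, so no participant or visit depends on the SCFA calculation. That limits the consequence, but an explicit 90% should still refer to the comparison in the aim.

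Two stronger readings are not supported. A reader might infer that the design has no power for any MM effect; the detectable differences above show otherwise, and a large MM effect would be found. A reader might also infer an error from the P = 0.1 reported in Section 1.0, because a paired t-test on these means, with ± as SD and n = 4, gives 0.17 and 0.24. The protocol does not name the test used, so nothing follows.

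**Conclusion.** The point holds for the 1-week crossover contrast. The stated 90% is the power to detect a difference as large as metformin's 3-month change, and it carries over to Aim 2 only if one week of MM adds about that much (roughly 85% of it for propionate, 105% for butyrate, with 20 pairs). Whether it does is unknown from the documents, so no single corrected power exists. At half the metformin change, power with 20 pairs would be about one third to one half.

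These figures rest on a two-sided paired test, on ± being an SD, and on variability in 4 youth on metformin alone carrying over to MM minus placebo. The last is weak. What is missing is a justified planning effect; the calculation itself is correct.

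**What to change.** In Section 5.1, delete the 90% power claim for SCFA and replace it with a statement along these lines:

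- No data are available on the MM-minus-placebo difference in stool SCFA.
- If the SD of the paired difference is 3.3 (propionate) and 5.72 (butyrate) µmol/g, the 95% CI half-width is about 2.4 / 4.1 with 10 pairs and 1.5 / 2.7 with 20. The difference detectable with 80% power is about 3.3 / 5.7 and 2.2 / 3.8.
- These SDs are an assumption borrowed from 4 youth on metformin alone and are very uncertain. Say explicitly whether ± is an SD.
- A non-significant 1-week result does not exclude differences inside the observed confidence interval.
- The open-label 4-week change has no concurrent placebo and is not covered by this calculation.

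The cost is one paragraph and a less favourable statement about the secondary outcome. The sample size, visits and analyses stay as they are.
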